Dosing for ASP8273, erlotinib or gefitinib may be interrupted or reduced (ASP8273 and erlotinib only) for any event if the investigator deems it necessary to ensure subject safety. Subjects requiring a treatment interruption should be re-evaluated not longer than 7 days from initial interruption and restarted on study drug as soon as clinically stable. The subject may be discontinued from treatment if there is an interruption of treatment for > 14 consecutive days despite optimal treatment of side effects. A discussion with the Medical Monitor should occur to confirm if the subject should continue on study treatment.

In the event of acute onset or worsening of pulmonary symptoms likely suggestive of ILD (dyspnea, cough, fever), study drug should be interrupted and a prompt investigation of these symptoms should occur and appropriate treatment initiated. If ILD is confirmed, study drug should be discontinued, and the subject should be treated appropriately per local standard of care.

Study drug should be interrupted if the subject experiences eye toxicity such as acute and severe eye pain or keratitis. Subjects with suspected keratitis should have study drug withheld until recovery and discontinued for persistent severe keratitis. Subjects with ocular toxicities should be evaluated by an ophthalmologist.

If the subject experiences severe hepatic impairment, study drug should be discontinued and the subject should be treated appropriately per local standard of care.

The table below summarizes ASP8273 dose modifications:

Dose level	ASP8273 dose (mg qd)
Starting dose	300
-1	200
-2	100

Subjects requiring a dose reduction may be re-escalated one dose level (i.e., subjects reduced to 100 mg may only be re-escalated to 200 mg). If the event leading to the reduction recurs, the subject should be reduced the lower dose level and not re-escalated again. If a grade 3 or 4 study drug-related toxicity persists or recurs after 2 dose reductions, the subject should be permanently discontinued from ASP8273 treatment. Additionally, if after resolution of a Grade 4 event requiring dose interruption and/or dose reduction, the event reoccurs at a G3 or higher the subject should be permanently discontinued from ASP8273.

Please refer to Section [5.1.2](#) of the protocol for detailed dose modification criteria.

The table below summarizes Erlotinib dose modifications:

Dose level	Erlotinib (mg qd)
Starting dose	150
-1	100
-2	50

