Grade 3	
 Interrupt dosing until the AE recovers to grade \leq 1 or baseline, then resume treatment at the same dose level or 1 dose level lower at the discretion of the investigator If Grade \geq 3 AST or ALT elevation recurs after resuming study drug at the same dose level, an additional rechallenge at a reduced dose may be considered, at the discretion of the investigator, once the AE recovers to grade \leq 1 or baseline. If Grade \geq 3 AST or ALT elevation recurs after resuming study drug at a reduced dose, discontinue study drug
Grade 4	
 Interrupt dosing until the AE recovers to grade \leq 1 or baseline At the discretion of the investigator, either discontinue study drug or resume study drug 1 dose level lower If Grade \geq 3 AST or ALT elevation recurs after resuming study drug at a reduced dose, discontinue study drug
Interstitial Lung Disease	
Any grade	
 If ILD is suspected, ASP8273 should be interrupted immediately pending diagnostic evaluation. If ILD is diagnosed, ASP8273 should be discontinued permanently and appropriate treatment instituted as necessary.
Other adverse events, including ocular toxicity	
Grade 3	
 Interrupt dosing until the AE recovers to grade \leq 1 or baseline, then resume treatment at the same dose level or 1 dose level lower at the discretion of the investigator If Grade \geq 3 AE recurs after resuming study drug at the same dose, an additional rechallenge at a reduced dose may be considered, at the discretion of the investigator, once the AE recovers to grade \leq 1 or baseline If Grade \geq 3 AE recurs after resuming study drug at a reduced dose, discontinue study drug
Grade 4	
 Interrupt dosing until the AE recovers to grade \leq 1 or baseline At the discretion of the investigator, either discontinue study drug or resume study drug 1 dose level lower If Grade \geq 3 AE recurs after resuming study drug at a reduced dose, discontinue study drug

¹ Hold ASP8273 and repeat AST and ALT within 1 day to confirm abnormal results before discontinuing subject from ASP8273 treatment.

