Any Grade	If ILD is suspected, erlotinib should be interrupted immediately pending diagnostic evaluation. If ILD is diagnosed, erlotinib should be discontinued permanently and appropriate treatment instituted as necessary.
Other Toxicities, including ocular toxicity	
Grade 1 or 2	None
Grade 3 ^{2,3}	Interrupt erlotinib until resolution to \leq grade 2 and then restart 1 dose level lower
Grade 4	Permanently discontinue erlotinib

Footnotes appear on next page

- ¹ Doses that have been reduced to 100 mg/day may be reescalated to 150 mg/day, but only if the toxicity that led to the dose reduction has abated or returned to baseline severity, and the investigator believes it is in the best interest of the subject. Doses that have been reduced to 50 mg/day may be reescalated to 100 mg/day, but only if the toxicity that led to the dose reduction has abated or returned to baseline severity, and the investigator believes it is in the best interest of the subject. **Doses that have been reduced to 50 mg/day may never be re-escalated to a dose higher than 100 mg/day.** Any subject who fails to tolerate treatment with 50 mg/day will be discontinued from erlotinib and enter the posttreatment period of the study.
- ² If the event does not resolve to \leq grade 2 by \leq 14 days, erlotinib will be discontinued.
- ³ Only if \geq 2 grade level change from baseline

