5.1.2.3 Gefitinib Dose Modification

There will be no dose reductions for subjects receiving gefitinib as it is only available as a single strength tablet. Below summarizes recommended therapy interruption for gefitinib; however, the locally approved label should be followed for additional guidance.

Gefitinib Dose Modification Criteria	
Toxicity (NCI CTCAE v4.03)	Dose Modification for Gefitinib
Diarrhea	
Persistent Grade 2 or \geq Grade 3	Interrupt gefitinib up to 14 days. Resume treatment when event resolves to Grade \leq 1 or baseline.
Skin Reactions	
\geq Grade 3	Interrupt gefitinib up to 14 days. Resume treatment when event resolves to Grade \leq 1 or baseline.
Interstitial Lung Disease	
Any Grade	In the event of acute onset or worsening of pulmonary symptoms suggestive of ILD (dyspnea, cough fever), gefitinib should be interrupted immediately pending diagnostic evaluation. If ILD is confirmed, gefitinib should be discontinued permanently and appropriate treatment instituted as necessary.
AST, ALT or bilirubin elevation	
\geq Grade 2	Interrupt gefitinib up to 14 days. Resume treatment when event resolves to Grade \leq 1 or baseline.
Other Toxicities, including ocular toxicity	
\geq Grade 3	Interrupt gefitinib up to 14 days. Resume treatment when event resolves to Grade \leq 1 or baseline.

If ILD, persistent severe keratitis, severe hepatic impairment or gastrointestinal perforation is confirmed, gefitinib should be discontinued, and the subject should be treated appropriately per local standard of care.

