5.1.4 Treatment Compliance

The dose of ASP8273 or erlotinib/ gefitinib administered to each subject will be recorded on the subject diary and entered in to the eCRF. Reasons for dose interruption, reduction or omission will also be recorded. This information, plus study drug accountability at every cycle will be used to assess compliance with the treatment.

Any subject who misses > 14 consecutive days of study drug dosing, on either treatment arm, may be discontinued from the study upon discussion between the investigator and sponsor's Medical Monitor.

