6 DISCONTINUATION

6.1 Discontinuation of Individual Subject(s)

A discontinuation is a subject who enrolled in the study and for whom study treatment is permanently discontinued for any reason.

The subject is free to withdraw from the study treatment and/or study for any reason and at any time without giving reason for doing so and without penalty or prejudice. The investigator is also free to terminate a subject's involvement in the study at any time if the subject's clinical condition warrants it.

The subject will be discontinued from the treatment period if any of the following occur:

- Subject develops radiological progressive disease (i.e., PFS#1) per RECIST v1.1 based on central confirmation of investigator assessment
 - If there is radiographic evidence of PD by investigator, however the investigator believes the subject is continuing to derive clinical benefit (asymptomatic and/or without worsening of performance status or overall health) from study drug, and an increase in tumor burden is not likely to affect vital organ function, the subject may remain on study drug until the next scheduled radiographic assessment which should occur after 56 days (± 7 days).
 - If the next radiographic assessment indicates PD per RECIST 1.1 which is confirmed by the central reviewer, then the subject must be discontinued from study drug.
 - In the rare event where PD suspected on initial assessment is not confirmed on subsequent scan by the investigator or central reviewer, the subject may continue in the study.
 - The investigator should make every effort to immediately submit radiographic assessments for central review when PD is either suspected or confirmed or uncertainty exists.
 - In case of PD determination by the investigator, however not confirmed by the central reviewer, and subject is progressing clinically and requires new anti-cancer treatment immediately, the subject should be discontinued.
- Subject is required to receive local or systemic anti-cancer treatment based on investigator's clinical opinion.
- Subject develops unacceptable toxicity
- Female subject becomes pregnant

- Investigator decides it is in the subject's best interest to discontinue including clinical progression
- Requirement for significant surgical procedure; however, if surgical procedure is for the resection of the primary or metastatic lesion, the subject may be eligible to continue on study treatment after discussion with the Medical Monitor

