- Significant deviation from the protocol or eligibility criteria
- Subject declines further treatment
- Subject is noncompliant with the protocol based on the investigator or Medical Monitor assessment
- Subject is lost to follow-up despite reasonable efforts by the investigator to locate the subject
- Death

The subject may be discontinued from the study if there is an interruption of treatment for > 14 consecutive days despite optimal treatment of side effects. A discussion with the Medical Monitor should occur to confirm if the subject should continue on study treatment.

Subjects who discontinue study drug and enter the posttreatment follow up period prior to reaching PFS#1 will be discontinued from the posttreatment period if any of the following occur:

- Subject develops radiological progressive disease (i.e., PFS#1) based on investigator assessment
- Subject initiates a new systemic anticancer treatment
- Subject misses 2 consecutive scheduled tumor assessments

The subject will be discontinued from the long-term follow-up period (for PFS#2) if any of the following occur:

- Subject initiates a new systemic anticancer treatment (3rd line)
- Subject exhibits evidence of PD from 2nd line therapy based on investigator assessment
- Subject declines further study participation (i.e., withdraws consent)
- Subject is lost to follow-up despite reasonable efforts by the investigator to locate the subject
- Death
- Sponsor ends long-term follow-up collection period

The subject will be discontinued from the survival follow-up period if any of the following occur:

- Subject declines further study participation (i.e., withdraws consent)
- Subject is lost to follow-up despite reasonable efforts by the investigator to locate the subject
- Death
- Sponsor ends survival follow-up period

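### Protocol 5.1.4 and 6.1 allow removal from the study after more than 14 consecutive days off drug, where 5.1.2 and the synopsis allow only stopping treatment; the two sections should say study treatment, so that follow-up continues

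*Protocol*

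**What the plan says.** The protocol states the rule for a gap of more than 14 consecutive days four times, with two different actions.

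- **Synopsis (Dose Modifications) and Section 5.1.2:** "The subject may be discontinued from treatment if there is an interruption of treatment for > 14 consecutive days".
- **Section 6.1:** "The subject may be discontinued from the study if there is an interruption of treatment for > 14 consecutive days".
- **Section 5.1.4 (Treatment Compliance):** a subject on either arm who misses that much dosing "may be discontinued from the study upon discussion between the investigator" and the sponsor's Medical Monitor.

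Section 6.1 opens with a definition: "A discontinuation is a subject who enrolled in the study and for whom study treatment is permanently discontinued for any reason". Directly after its 14-day sentence comes: "A discussion with the Medical Monitor should occur to confirm if the subject should continue on study treatment". The section then lists separate exits for the posttreatment, long-term and survival follow-up periods.

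Section 2.2.1, Section 5.3 and Table 2 footnote 1 keep a subject who stops drug before PFS#1 on 56-day imaging. After PFS#1 the subject moves to long-term follow-up for PFS#2, and after PFS#2 to survival follow-up.

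**The concern.** In this protocol, leaving treatment and leaving the study are different things. Section 6.1 treats withdrawal from one or the other as separate choices and gives each follow-up period its own exit list. A site cannot assume that the two phrases mean the same.

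If a site acted on the study wording, 56-day imaging and survival contact would stop. Under Section 7.4.1.1 an event-free subject would then be censored for PFS at the last scan. Later information would often not repair this, because progression or death after two missed assessments is also censored; SAP Section 6.1.1 defines that as a gap of more than 140 days between assessments. For OS, Section 7.4.2.1 is meant to count every death on or off drug, but a subject no longer contacted is censored at the last date known alive.

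Such exits would not be random. The 6.1 rule concerns interruptions that persist despite managing side effects, and 5.1.4 concerns compliance. Long gaps may be related to prognosis. They may also differ in frequency between arms: ASP8273 and erlotinib have two dose reductions available, gefitinib has none, and the trial is open-label. Censoring of this kind could be informative.

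**Working it through.** No design figure is in dispute, so the main check is a comparison of texts. A short calculation then shows why power is not the issue.

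**1. Same trigger, two actions.** Two statements (synopsis, 5.1.2) stop treatment; two (5.1.4, 6.1) remove the subject from the study. The 6.1 sentence matches the 5.1.2 sentence except for what the subject is discontinued from. That looks like a drafting slip rather than a second rule.

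**2. What 6.1 means.** Three features of the section point to treatment only:

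- its definition of a discontinuation is a permanent stop of study treatment;
- its next sentence asks about continuing on study treatment;
- none of its exits from posttreatment, long-term or survival follow-up is a dosing gap.

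Read whole, 6.1 largely corrects itself.

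**3. What 5.1.4 means.** It has no definition, no follow-on sentence about treatment and no pointer to follow-up. Read alone, it permits removal from the study.

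**4. Whether the drug tables settle it.** They do not.

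- ASP8273 (Table 4) sets no time limit: for Grade 3 or 4 events under several headings it says "Interrupt dosing until the AE recovers to grade" 1 or lower, or baseline.
- Gefitinib (5.1.2.3) says "Interrupt gefitinib up to 14 days. Resume treatment when event resolves to Grade" 1 or lower, or baseline, without saying what follows if 14 days pass.
- Erlotinib (Table 6, footnote 2) says "14 days, erlotinib will be discontinued", but its trigger is an event that has not resolved to Grade 2 or lower within 14 days. That is not the same as 14 days of missed doses.

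**5. Power, for context.** Inputs from protocol Section 7.1: 420 events, HR 0.667, 1:1 allocation, 1-sided alpha 0.025.

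Schoenfeld: power = Φ(√d × |ln HR| / 2 − 1.960) = Φ(20.494 × 0.40497 / 2 − 1.960) = Φ(2.190) = 98.6%, against the stated 98.7%. The protocol figure reproduces.

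The documents give no removal rate. As an assumption only, suppose removals cost a share of the 420 events and these were not replaced:

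| Share of events lost | Events | Power |
|---|---|---|
| 1% | 415.8 | 98.5% |
| 2% | 411.6 | 98.4% |
| 5% | 399 | 98.1% |
| 10% | 378 | 97.6% |

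Because the protocol ties the analysis to the event count, removals would mainly delay it. As a unit conversion, each 1% of subjects removed is 0.01 × 600 = 6 subjects.

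**The case against.** The strongest reply is that context already resolves the wording. For 6.1 this mostly stands. A reader might infer from the quoted sentence that the protocol plans to drop these subjects from imaging and survival contact. The section's own definition, next sentence and exit lists do not support that. The reply does not reach 5.1.4.

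A second reply is that the usual causes of a long gap are already treatment-period exits for every drug: unacceptable toxicity, the investigator's judgement of best interest, declining further treatment, and noncompliance. This also stands. It would be too strong to say that ASP8273 and gefitinib subjects have no other governing text. Those exits do not, however, cancel an explicit sentence that names the study.

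Third, the action is optional and goes through the Medical Monitor, and SAP Section 7.2.1 tabulates discontinuation by period, primary reason and arm. Removals should therefore be few and partly visible. Tabulating them does not recover the lost follow-up.

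Fourth, Section 6.1 separately lets the investigator end a subject's involvement when the clinical condition warrants it. Rewording the 14-day rule leaves that discretion in place, so this route out of the study would remain.

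**Conclusion.** The inconsistency is real and sits in an operative rule. It is clear-cut in 5.1.4; in 6.1 the wording is wrong but the intent can be recovered. That treatment-only discontinuation is intended is an inference, though a well-supported one.

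The effect cannot be sized, because the documents give no rate of gaps over 14 days and none of removals. It is probably small. A reader might infer a material bias in PFS or OS, or a loss of power. The documents support neither: the link to prognosis and the difference between arms are possibilities rather than reported facts, and the power figures above barely move even under the assumed losses.

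The change is still worth making, since it protects follow-up for the primary endpoint and a key secondary endpoint at almost no cost.

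**What to change.** In Sections 5.1.4 and 6.1, change the action to discontinuation from study treatment. Add a cross-reference in both places to Section 2.2.1 and Table 2, so that these subjects enter the existing periods in order: posttreatment follow-up with 56-day imaging, long-term follow-up for PFS#2, then survival follow-up, each under the exits already listed. A cross-reference is safer than restating the sequence, because a short restatement could skip the long-term period.

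The decision to stop drug and the investigator's separate discretion in 6.1 do not change. Appendix 12.2 also speaks of discontinuation from the study, but its trigger is unexplained liver test elevation, so it need not be part of this change.

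The cost is a wording change in two sections of an amendment, plus continued imaging and contacts, already scheduled in Table 2, for the subjects concerned.

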6.2 Discontinuation of the Site

If an investigator intends to discontinue participation in the study, the investigator must immediately inform the sponsor.

6.3 Discontinuation of the Study

The sponsor may terminate this study prematurely, either in its entirety or at any study site, for reasonable cause provided that written notice is submitted in advance of the intended termination. Advance notice is not required if the study is stopped due to safety concerns. If the sponsor terminates the study for safety reasons, the sponsor will immediately notify the investigator and subsequently provide written instructions for study termination.

7 STATISTICAL METHODOLOGY

The statistical analysis will be coordinated by the responsible biostatistician of APGD. A Statistical Analysis Plan (SAP) will be written to provide details of the analysis, along with specifications for tables, listings and figures to be produced. The SAP will be finalized before enrollment of the first subject. Any changes from the analyses planned in SAP will be justified in the clinical study report (CSR).

Prior to Database Lock, a Final Review of Data and TLFs Meeting will be held to allow a review of the clinical trial data and to verify the data that will be used for analysis set classification. If required, consequences for the statistical analysis will be discussed and documented. A meeting to determine analysis set classifications may also be held prior to database lock.

In general, all data will be summarized with descriptive statistics (number of subjects, mean, standard deviation, minimum, median and maximum) for continuous endpoints, and frequency and percentage for categorical endpoints.

7.1 Sample Size

Approximately 600 subjects will be randomized in a 1:1 ratio to 2 treatment arms: Arm A (ASP8273) and Arm B (erlotinib or gefitinib). Randomization will be stratified by ECOG PS (0, 1 or 2), EGFR mutation type (exon 19 deletion or mutation in exon 21 [L858R]), TKI chosen (erlotinib versus gefitinib) and race (Asian versus nonAsian). Assuming HR=0.667 (median PFS in Arm A and Arm B are 15.6 months and 10.4 months, respectively), a total of 420 PFS events will provide approximately 98.7% power to detect a statistically significant difference at type I error rate of 1-sided 0.025.

7.2 Analysis Set

Detailed criteria for analysis sets will be laid out in Classification Specifications and the allocation of subjects to analysis sets will be determined prior to database hard-lock.

7.2.1 Full Analysis Set (FAS)

The full analysis set will consist of all subjects who are randomized. This will be the primary analysis set for efficacy analyses.

7.2.2 Per Protocol Set (PPS)

The per protocol set will consist of the subset of the FAS who do not meet criteria for PPS exclusion. These criteria are to capture relevant nonadherence to the protocol and will be defined in the SAP. In addition, subjects in the PPS are required to have both baseline imaging and at least 1 postbaseline imaging scan. The PPS will be a secondary analysis set for efficacy analyses. Select demographic and baseline characteristics may also be summarized for the PPS.

7.2.3 Safety Analysis Set (SAF)

For the statistical summary of the safety data, the safety analysis set (SAF) will be used. The SAF consists of all subjects who take at least 1 dose of study medication, and will be used for safety analyses.

7.2.4 Pharmacokinetic Analysis Set (PKAS)

The pharmacokinetic analysis set (PKAS) consists of the subset of the SAF population for which at least one plasma concentration data is available for whom the time of dosing on the previous day of sampling is known. Additional subjects may be excluded from the PKAS at the discretion of the pharmacokineticist. Any formal definitions for exclusion of subjects or time-points from the PKAS will be documented in the Classification Specifications and determined in the Classification Meeting.

